3.4 Safety outcomes

3.4.1 Adverse events

Adverse events will be collected throughout the treatment period and including the follow-up period (Visit 6).

Serious AEs (SAEs) will be collected from the time of informed consent (Visit 1) whereas AEs will be collected from randomisation (Visit 2), throughout the treatment period and including the follow-up period (Visit 6).

The latest version of the Medical Dictionary for Regulatory Activities (MedDRA) dictionary will be used to code the AEs. The investigator's verbatim term for each AE will be mapped to a system organ class (SOC) and preferred term (PT) from MedDRA. All coding will be performed by the Medical Coding Team.

Treatment emergent adverse event (TEAE) is defined as an AE that started on or after treatment start date and within 14 days after treatment stop date.

3.4.2 Vital signs

Vital signs (systolic and diastolic blood pressure, pulse rate and body temperature, all three in a lying or sitting position after 5 minutes of rest) will be taken at the times indicated in the Study Plan and Timing of Procedures (refer to protocol Table 1).

Change from baseline in vital signs to each post-baseline assessment will be calculated. There will be no imputation for missing values.

Observed values and change from baseline for all assessments will be compared to the relevant AstraZeneca defined reference ranges (see Appendix B – AstraZeneca defined reference ranges for vital signs) and all values (observed and change) falling outside the reference ranges will be flagged. The minimum and maximum values post-baseline will be derived for SBP, DBP, pulse rate and temperature based on pre-defined criteria provided by AZ in Appendix B (low, normal, high).

3.4.3 ECG

Twelve-lead ECGs will be obtained at the times indicated in the Study Plan and Timing of Procedures (refer to protocol Table 1). An overall evaluation (normal, abnormal not clinically significant, and abnormal clinically significant) with a reason for abnormality will also be recorded.

3.4.4 Laboratory data

Blood and urine samples for determination of clinical chemistry, haematology, endocrinology, and urinalysis will be taken at the times indicated in the Study Plan and Timing of Procedures (refer to protocol Table 1).

The parameters to be determined are presented in Appendix C – Laboratory Parameters.

Changes from baseline in continuous laboratory variables to each post-baseline assessments will be calculated.

Observed values will be compared to the central laboratory reference ranges and all observed values falling outside these reference ranges will be flagged.

For laboratory results below or above the limit of quantification:

- Assign as equal to the limit of quantification, for example < 100 mL will be assigned as 100 mL.

The minimum and maximum values post-baseline will be derived based on reference ranges provided in the most recent Covance lab manual available at database lock (low, normal, high). A listing of normal ranges will be provided.

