5.2 Safety assessments

5.2.1 Laboratory safety assessments

Blood and urine samples for determination of clinical chemistry, haematology, and urinalysis will be taken at the times indicated in the Study Plan (see Section 4).

Additional safety samples may be collected if clinically indicated at the discretion of the Investigator. The date, time of collection and results (values, units and reference ranges) will be recorded on the appropriate eCRF.

A central laboratory will be used in this study (Covance Central Laboratory Services) but for the safety lab panel at Visit 1 also local labs will be used. The clinical chemistry, haematology and urinalysis can therefore be analyzed at a local laboratory at or near to the Investigator site both at Visit 1 and if needed on ad hoc basis if deemed necessary by the investigator. Sample tubes and sample sizes may vary depending on laboratory method used and routine practice at the site. Reference values from all labs used in the study will be included in the eCRF.

The following laboratory variables will be measured:

Table 2 Laboratory Safety Variables

Haematology/Haemostasis (whole blood)	Clinical Chemistry (serum or plasma)
B-Haemoglobin (Hb)	S/P-Creatinine
B-Leukocyte count	S/P-Bilirubin, total
B-Leukocyte differential count (neutrophils, lymphocytes, monocytes, eosinophils and basophils)	S/P-Alkaline phosphatase (ALP)
B-Platelet count	S/P-Aspartate transaminase (AST)
Erythrocyte sedimentation rate, ESR	S/P-Alanine transaminase (ALT)
	S/P-Albumin
	S/P-Potassium
Urinalysis (dipstick)	S/P-Calcium, total
U-Hb/Erythrocytes/Blood	S/P-Sodium

U-Protein/Albumin	S/P-Creatine kinase (CK)
U-Glucose	S/P-C-reactive protein (CRP)
	S/P-Low density lipoprotein (LDL)
	S/P-High density lipoprotein (HDL)
	S/P-Free fatty acids (FFA)
Endocrinology	S/P-fasting glucose ^b
FSH ^a	S/P-insulin

^a Only at Visit 1 for women under the age of 50 considered to be post-menopausal to determine that the hormones are in the post-menopausal range

^b Fasting glucose on Visit 2, Visit 4 and Visit 5.

The Investigator should make an assessment of the available results with regard to clinically relevant abnormalities. The laboratory results should be signed and dated and retained at centre as source data for laboratory variables. For information on how AEs based on laboratory tests should be recorded and reported, see Section 6.3.

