3.1.4 C-reactive protein (CRP)

CRP (mg/L) is collected at the local laboratory for Visit 1. Central laboratory will be used for Visit 2, 4, 5 and 6. Visit 3 will be a phone call only, therefore no laboratory testing will take place on that visit.

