4.8.6.3 Laboratory variables

Observed results and changes from baseline at each scheduled visit will be summarised for each quantitative haematology and clinical chemistry parameter. The following rules will be applied if more than one observation is available for a subject at a single visit:

- If there are two or more observations at the same scheduled visit, the observation closest to the target day will be used in the summary
- If two observations are equidistant from the target day and the ties are on different sides of the target day, the observation with the earlier assessment date will be used in the analysis.
- If two observations are equidistant from the target day and the ties located on the same sides of the target day (i.e. more than one observation for the same day but different time), the observation with the earlier (if the assessment day is equal or larger than the target day) or later (if the assessment day is smaller than the target day) assessment time will be used in the analysis.

A shift table from baseline to minimum value post-baseline will be provided for qualitative haematology and chemistry values (low, normal, high). Similarly, a shift table from baseline to maximum value post-baseline will be provided for qualitative haematology and chemistry values (low, normal, high). Low, normal and high will be defined based on Covance reference ranges.

To identify potential Hy's Law cases, a listing of subjects who have ALT or AST $\geq 3 \times$ ULN and total bilirubin $\geq 2 \times$ ULN will be presented. This listing will include all visits for this subset of subjects.

A plot will also present maximum post-baseline ALT/AST versus maximum post-baseline total bilirubin, expressed as multiples of ULN.

Line plots of the mean (+/- SE) of the following clinical chemistry and haematology parameters will be presented in a figure: CRP, glucose, potassium, ESR, haemoglobin, platelets and leukocytes.

Key subject information for haematology and chemistry results outside the Covance reference ranges will be provided, along with an overview of number and percentage of subjects with results outside the reference ranges post-baseline.

Pregnancy test results will only be listed for eligible subjects of childbearing potential.

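### The SAP grades laboratory results only on central-laboratory ranges, although Visit 1, some ad hoc and all ESR results can come from local or site laboratories

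*SAP*

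**What the plan says.** **Grading.** SAP 3.4.4 states: "Observed values will be compared to the central laboratory reference ranges and all observed values falling outside these reference ranges will be flagged". For the minimum and maximum after baseline, the same section takes the limits from "reference ranges provided in the most recent Covance lab manual available at database lock". SAP 4.8.6.3 repeats the choice for the shift tables: "Low, normal and high will be defined based on Covance reference ranges". Neither section makes an exception for results from another laboratory.

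**Where samples are analysed.** Protocol 5.2.1 names a central laboratory but adds that "for the safety lab panel at Visit 1 also local labs will be used". It says the safety panels can be analysed locally "both at Visit 1 and if needed on ad hoc basis if deemed necessary by the investigator". Footnote c of protocol Table 1 marks the Visit 1 clinical laboratory evaluations as local. SAP 3.1.4 agrees for one analyte: "CRP (mg/L) is collected at the local laboratory for Visit 1", with central testing at Visits 2, 4, 5 and 6. Protocol Table 1 also lists ESR as measured at site at Visits 1, 2, 4, 5 and 6, and Table 2 places ESR among the haematology safety variables.

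**Ranges collected.** Protocol 5.2.1 says: "Reference values from all labs used in the study will be included in the eCRF". No SAP rule uses the local ones.

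**The concern.** Reference limits belong to the laboratory and method that produced the result. Protocol 5.2.1 itself recognises that methods vary between laboratories. If a local or site result is judged against central limits, a value that is normal for its own laboratory can be flagged, and an abnormal one can pass.

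Safety is a stated objective, and this is the first study of the drug in patients. Arms are small: SAP 1.3 gives about 20 per group as the plan and 10 per group as the number later agreed. One patient moved between cells of a shift table changes that arm's percentage by 1/20 = 5 points or 1/10 = 10 points. Additional samples are taken when clinically indicated, so a misgraded ad hoc result could be one that a reader of the listings cares about.

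**Working it through.** The plan gives no figure to reproduce. The check compares the source of each result with the source of its limits, output by output.

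| Output | Limits named in the SAP | Can a local or site result enter? |
|---|---|---|
| Flags on observed values (3.4.4) | Central | Yes: Visit 1 results, ad hoc results run locally, ESR at every clinic visit |
| Baseline class in shift tables (4.1.2, 4.8.6.3) | Covance | ESR: yes. Others: when the Visit 2 pre-dose value is missing and a Visit 1 or unscheduled local value replaces it |
| Class of post-baseline minimum and maximum (3.4.4, 4.8.6.3) | Covance manual at database lock | ESR at Visits 4, 5 and 6: yes. Visit 1: no, it precedes baseline. Ad hoc: unclear |
| Overview of post-baseline out-of-range results (4.8.6.3) | Covance, from the same sentence | As for the minimum and maximum |
| By-visit summaries of values and changes | None | No limit is used |
| Hy's Law listing and ALT/AST-versus-bilirubin plot (4.8.6.3) | Multiples of ULN; laboratory not named | Cannot be settled from the text |

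**Ad hoc samples and the extremes.** SAP 4.1.3 says that scheduled visits are used for analysis, which suggests that unscheduled samples stay out. SAP 3.4.4 does not say so for the minimum and maximum. The rule in 4.8.6.3 for several observations at one visit governs the by-visit summaries and is not stated to govern the extremes.

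**ESR.** This is the one variable for which scheduled samples are affected both at baseline (Visit 2) and afterwards (Visits 4, 5 and 6). Its place in the shift tables rests on protocol Table 2, which classes it as haematology, and on SAP 4.8.6.3, which plots it with the chemistry and haematology parameters. The documents do not show whether the Covance manual holds an ESR range at all.

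**When a grade is wrong.** Let U_local and U_central be the upper limits of the two laboratories and k the multiple tested. A local result x is misgraded only if it lies between k × U_local and k × U_central. The documents give no limits, so the following ALT limits are assumptions that show only the mechanism:

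- Local 45 U/L, central 33 U/L. At k = 1, a value above 33 and up to 45 is flagged high although it is within its own range. At k = 3, 3 × 33 = 99 and 3 × 45 = 135, so whole-number values from 99 to 134 cross the threshold on the central limit only. For example, 110/45 = 2.44 and 110/33 = 3.33.
- Local 33 U/L, central 45 U/L. The same intervals apply in reverse: elevations on the local range are missed.
- Equal limits. No result is misgraded.

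**The case against.** The strongest case on the other side is that little of consequence is touched.

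- **Visit 1.** A reader might infer that one in five scheduled panels per patient distorts the safety comparison. The documents do not support that. A screening value cannot be a post-baseline extreme, baseline is normally the Visit 2 pre-dose value, and by-visit means use no range. What remains is mainly a listing flag.
- **Ad hoc samples.** A reader might infer that all of these are local and all feed the shift tables. The protocol only permits local analysis, and SAP 4.1.3 points away from unscheduled values.
- **Hy's Law outputs.** A reader might infer that these use the wrong ULN. SAP 4.8.6.3 does not name the ULN source; its sentence on Covance limits defines the low, normal and high classes. The listing also requires bilirubin of at least 2 × ULN, so a shift in the ALT multiple alone does not show that any patient enters or leaves it.
- **Patient care.** Investigators review available results for clinical relevance during the study, and liver elevations are referred to protocol Appendix D. The SAP plans no formal statistical analysis of safety data.

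All four limits stand. They narrow the point without removing it. The SAP states a positive rule that does not fit some of the data it governs, and ESR escapes the first two arguments because its site measurements are scheduled before and after the start of treatment.

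**Conclusion.** The mismatch is real and limited. It reaches listing flags for Visit 1 and local ad hoc results, the baseline class when Visit 2 is missing, and ESR flags and shifts at scheduled visits. It reaches post-baseline extremes of other variables only if unscheduled samples are included. Central limits suit the scheduled samples at Visits 2, 4, 5 and 6 other than ESR; central testing there is stated expressly for CRP and is taken to hold for the rest of the panel.

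It would go too far to say that every local result is misclassified. That needs limits that differ and a value between them. Without the ranges, the number of misgraded results cannot be estimated, and it could be zero. No efficacy result depends on these grades. Because the local ranges are already due to be held and the correction is simple, it should be made before the outputs are produced.

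**What to change.** Amend SAP 3.4.4 and 4.8.6.3 as follows:

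1. Grade each result (flags and low/normal/high classes) against the range of the laboratory that analysed it, as recorded in the eCRF. For ESR, use the site's range.
2. Apply the same laboratory's ULN in the Hy's Law listing and the ALT/AST-versus-bilirubin plot, and say so.
3. Identify local and site results in the listings.
4. State whether unscheduled local results enter the post-baseline minimum and maximum outputs, so that 3.4.4 and 4.1.3 agree.

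The cost is SAP wording and a programming merge on the laboratory identifier. No new data should be needed, since protocol 5.2.1 already places the ranges in the eCRF. Two things should be confirmed first: that ESR ranges from the sites are among them, and, if any laboratory changed its limits during the study, that the eCRF shows which limits applied to each sample.

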3.5 Exploratory outcomes

3.5.1 Biomarkers

Whole blood and serum/plasma will be collected to enable relevant analyses such as, effects on bone, metabolism and HPA axis by assessment of:

- Individual LPS-stimulated WB TNF α levels (pg/mL).
- Individual plasma cortisol (nmol/L) AUEC $_{(0-6)}$.
- Change from baseline for morning plasma cortisol (nmol/L) at Day 15 and follow-up visit.

For each subject, the total AUEC at Day 1 and Day 15 will be calculated for plasma cortisol. Plasma cortisol is collected pre-dose only on Day 1 at 0, 1, 2, 3, 4 and 6 hours, and then pre-dose and post-dose at 1, 2, 3, 4 and 6 hours on Day 15. Each AUEC will be calculated using trapezoids as

$$AUEC = \sum_{i=1}^6 (t_{i+1} - t_i) \frac{y_{t_{i+1}} + y_{t_i}}{2}$$

The summation is over all available time points. The y_t are the concentration measurements. If any two consecutive measurements are missing, or if one or both of the measurements at time 0 for Day 1, pre-dose for Day 15 or 6 hours on either day are missing, then the AUEC for that day is missing. However, if the measurement at any single intermediate number of hours is missing, the AUEC will be calculated using linear interpolation.

For example, if measurements are available at only 0, 1, 2, 3 and 6 hours for Day 1, then

$$AUEC = (1 - 0) \frac{y_1 + y_0}{2} + (2 - 1) \frac{y_2 + y_1}{2} + (3 - 2) \frac{y_3 + y_2}{2} + (6 - 3) \frac{y_6 + y_3}{2}$$

3.5.2 Other exploratory outcomes

DAS28 will be used for additional comparison between AZD9567 and Prednisolone 20mg, by means of:

- European League Against Rheumatism (EULAR) response criteria.
- DAS28 remission.

- Clinically important change in DAS28 score.
- Low disease activity based on DAS28 score.

Improvement (can be either positive or negative and is defined as post-baseline minus baseline) in DAS28 score will be calculated at each post-baseline scheduled assessment and categorised using the EULAR response criteria in [Table 1](#). Good, moderate or no response will be determined by the DAS28 score at Day 8, 15 and 28 against the level of improvement (mean change from baseline in DAS28 at Day 8, 15 and 28).

Table 1 DAS28 EULAR Response

DAS28 improvement			
Background DAS28(CRP) Score at Time of DAS28 Improvement Assessment	Level of Improvement from Baseline		
	> 1.2	≥ 0.6 to ≤ 1.2	< 0.6
< 3.2	Good response	Moderate response	No response
≥ 3.2 to ≤ 5.1	Moderate response	Moderate response	No response
> 5.1	Moderate response	No response	No response

DAS28: Disease Activity Score in 28 joints. DAS28(CRP): Disease Activity Score in 28 joints using C-reactive protein/erythrocyte sedimentation rate.

DAS28 remission:

- DAS28 score < 2.6

Clinically important change:

- Improvement from baseline in DAS28 score > 1.2

Low disease activity:

- DAS28 score ≤ 3.2

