3.1 Inclusion criteria

For inclusion in the study subjects should fulfil the following criteria:

- 1 Provision of informed consent prior to any study specific procedures
- 2 Male and female patients aged 18 through 80 years at screening
- 3 Established RA diagnosis according to the 2010 American College of Rheumatology (ACR)/EULAR classification or the 1987 criteria
- 4 Active RA (DAS28-CRP score ≥ 3.2) with at least 3 swollen joints and 3 tender joints using the DAS28 joint count

- 5 Patients must have been on stable dosing of conventional and/or s.c./i.v biological DMARDs for the last 8 weeks prior to Visit 1
- 6 CRP levels >5mg/L at screening if seronegative for RF and anti-CCP Ab, or >2mg/L if seropositive for either marker
- 7 BMI between 18 and 35 (inclusive)
- 8 Negative pregnancy test (serum) for female subjects of childbearing potential.
- 9 Female subjects must be 1 year post-menopausal, surgically sterile, or using an acceptable method of contraception (defined as a barrier method in conjunction with a spermicide) for the duration of the study, for details refer to Section 3.1.1
- 10 Male subjects must be surgically sterile or using an acceptable method of contraception (defined as barrier methods in conjunction with spermicides) for the duration of the study (from the time they sign consent) and for 1 month after the last dose of IMP to prevent pregnancy in a partner.
- 11 Subjects who are blood donors should not donate blood during the study and for 3 months following their last dose of IMP.

For inclusion in this genetic research, subjects must fulfil all of the inclusion criteria described above **and**:

- 12 Provide informed consent for the genetic sampling and analyses.

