4.4 Missing primary and secondary variables

4.4.1 Missing DAS28 (CRP) components

DAS28-CRP will be set to be missing if one or more components as defined above are missing. Higher DAS28-CRP scores indicate more severe symptoms and greater functional impairment

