6. CHANGES OF ANALYSIS FROM PROTOCOL

Table 2 Summary of changes from protocol

Reference	Protocol	Change	Justification
SAP Section 1.1.4	Section 2.4.	
The following exploratory endpoints will be included:
 
• European League Against Rheumatism (EULAR) response criteria.• DAS28 remission.• Clinically important change.• Low disease activity.	Additional endpoints considered important for efficacy interpretation by study team.
SAP Section 1.3	Section 8.2.	
Comparison to traditional hypothesis testing has been removed and replaced with a statement that the study is “not sufficiently powered to support hypothesis testing”.
 
The sample size of “n=18” per arm has been updated to “n=10” per arm.
	
Power of the study expected to be lower than that stated in the protocol, given the sample size and expected effect size. Wording updated to remove power calculation.
 
Update to n reflects agreement to close recruitment early. Hence a reduced n per arm was agreed.

SAP Section 4.2.1	Section 8.5.1	Concluded that the difference in mean CFB in DAS28 of AZD9567 - mean CFB in DAS28 of Prednisolone will show a better efficacy if the observed difference negative (less than 0) instead of positive (larger than 0).	Lower DAS28 score is better.

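### SAP 3.5.2 subtracts DAS28 'improvement' the wrong way round, so no improving patient can be a EULAR responder or show a clinically important change

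*SAP*

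**What the plan says.** SAP 3.5.2 (Other exploratory outcomes) fixes the order of subtraction: "Improvement (can be either positive or negative and is defined as post-baseline minus baseline) in DAS28 score will be calculated" at each scheduled visit after baseline. SAP Table 1 bands this value as above 1.2, 0.6 to 1.2, or below 0.6, and crosses it with the DAS28 score at the visit. For a score below 3.2, the three bands read "Good response Moderate response No response". Clinically important change is defined on the same scale: "Improvement from baseline in DAS28 score > 1.2". The level of improvement is also described as the "mean change from baseline in DAS28 at Day 8, 15 and 28".

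On direction, SAP 4.4.1 says "Higher DAS28-CRP scores indicate more severe symptoms and greater functional impairment". SAP section 6 reverses the sign of the protocol's primary decision rule and gives as its reason "Lower DAS28 score is better".

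SAP 4.3.3.5 reports these outcomes as counts and percentages by arm and visit up to Day 28, without tests. Protocol 5.1.1 has the same response table but gives no order of subtraction.

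**The concern.** The cut-offs work only if improvement is positive when the score falls. With post-baseline minus baseline, a fall is negative and always lands in the lowest band. Nothing in the SAP calls for an absolute value or a change of sign before Table 1 is used. The protocol leaves the order open, so the SAP introduces the fault. The SAP found and corrected a DAS28 sign problem in the primary rule but made no matching correction here.

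The wording has a second fault. It ties the level of improvement to a mean change, although response is a class assigned to each patient.

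Two of the four DAS28 outcomes that the SAP added are affected, at Days 8, 15 and 28. Section 6 justifies adding them by their value for interpreting efficacy. SAP 1.3 says that 10 per group was agreed and is too few for hypothesis testing, so readers are likely to lean on descriptive responder rates.

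**Working it through.** The documents give no expected response rate, so there is no planned figure to reproduce. The check applies the written rule and compares it with the same rule after the sign is corrected.

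**Inputs.** Order of subtraction, Table 1 and the 1.2 cut-off: SAP 3.5.2. Direction of the score: SAP 4.4.1 and section 6. Entry threshold: Protocol 3.1, "Active RA (DAS28-CRP score ≥ 3.2) with at least 3 swollen joints and 3 tender joints using the DAS28 joint count".

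**General argument.** Let b be the baseline score and p the later score. As written, improvement is I = p - b.

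- If the patient improves, p < b, so I < 0 < 0.6. Every row of Table 1 gives no response in that column, and I > 1.2 fails.
- A good response needs p < 3.2 and p - b > 1.2, so b < 3.2 - 1.2 = 2.0. This is impossible for a baseline at or above 3.2.
- A moderate response needs a rise of at least 0.6 ending at or below 5.1, or a rise above 1.2 at any score.
- Clinically important change needs a rise above 1.2.

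**Single patients (no assumptions needed).**

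| Baseline to visit | As written: value, EULAR, important change | Sign corrected: value, EULAR, important change |
|---|---|---|
| 5.0 to 3.0 | -2.0, none, no | +2.0, good, yes |
| 5.5 to 4.0 | -1.5, none, no | +1.5, moderate, yes |
| 4.5 to 3.7 | -0.8, none, no | +0.8, moderate, no |
| 4.0 to 4.7 | +0.7, moderate, no | -0.7, none, no |
| 3.5 to 5.0 | +1.5, moderate, yes | -1.5, none, no |
| 4.8 to 5.6 | +0.8, none, no | -0.8, none, no |

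**Grid.** Take baseline 3.2 to 8.0 and visit score 1.0 to 8.0 in steps of 0.1: 49 x 71 = 3479 pairs, of which 2254 improve, 49 are unchanged and 1176 worsen.

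- As written, all 2254 improving pairs are non-responders on both outcomes. Of the worsening pairs, 666 + 77 = 743 are moderate responses and 203 + 230 = 433 are none. The 666 that rise by more than 1.2 also count as clinically important change.
- Sign corrected, all 1176 worsening pairs are non-responders. The improving pairs split into 1000 good, 869 moderate and 385 none, and 1666 meet clinically important change.

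**Illustrative rates (assumed values, not in the documents).** Take the change d = p - b as normal with mean m and SD s. For clinically important change:

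- as written, P(d > 1.2) = 1 - Φ((1.2 - m)/s);
- as intended, P(d < -1.2) = Φ((-1.2 - m)/s).

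With m = -1.0 and s = 1.0 these are 1 - Φ(2.2) = 1.4% and Φ(-0.2) = 42%. Over m from -0.5 to -1.5 and s from 0.8 to 1.2, the rate is 0% to 8% as written and 19% to 65% as intended.

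For EULAR response, a simulation also assumed a baseline of mean 4.8 and SD 0.9, limited to 3.2 or above. With m = -1.0 and s = 1.0:

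- as intended, good is 25% to 26% and moderate about 38%, about 63% together before rounding;
- as written, good is 0% and moderate about 2.5%, all of them patients who got worse.

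The small spread reflects how the baseline limit is imposed. With m = -0.8, -1.0 and -1.3 at SD 1.0, good plus moderate is 56%, 63% and 74% as intended, against 3.9%, 2.5% and 1.3% as written. Widening the SD to 0.8 to 1.2 over the same means gives 55% to 78% against 0.3% to 6.6%.

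**The case against.** The strongest reply is that little depends on these outcomes. They are exploratory, reported as counts and percentages, and feed no decision rule. The primary MMRM, its ANCOVA sensitivity analysis, the component analyses and the ACR responses are untouched. So are remission and low disease activity, which use the score itself. This is correct, and it limits the damage to two descriptive outcomes.

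The intended direction can also be recovered. The table is headed as improvement, its best cell pairs a low score with a large improvement, and the SAP says elsewhere that lower is better. A programmer may well apply the usual direction, or notice that a good response never occurs. That lowers the practical risk, but the correct output would then depend on departing from the written rule.

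Two limits on the claim also stand. Not every worsening patient becomes a responder: on the grid, 433 of 1176 worsening pairs remain non-responders. The main effect is that nearly everyone is classed as a non-responder; the two arms do not exchange places. The percentages rest on assumed means, SDs and baseline; the single-patient examples do not.

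The mean-change wording is secondary, because reporting counts and percentages already implies classification by subject.

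**Conclusion.** The concern holds. As written, no patient whose DAS28 falls can be a EULAR responder or show a clinically important change. All responders on either outcome would be patients whose score rose by at least 0.6, and a good response cannot occur with a baseline of 3.2 or more. This follows from the SAP's own text and needs no assumption.

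The size in percentages does depend on assumptions. For a mean change of -1.0 with SD 1.0, clinically important change is 1.4% instead of 42%. In an arm of 10 that is 0.014 x 10 = 0.14 patients expected instead of 0.42 x 10 = 4.2. The primary and secondary analyses are unaffected. The rule should still be corrected before these outputs are programmed, because it gives the wrong class on outcomes that the SAP presents as useful for judging efficacy.

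**What to change.** In SAP 3.5.2, define improvement as baseline minus post-baseline, so that a positive value means a better score. State that each subject's own value at the visit is classified, and delete 'mean' from the description of the level of improvement. Table 1 and the 1.2 cut-off then work unchanged.

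An equivalent option is to keep change as post-baseline minus baseline and rewrite the bands as below -1.2, -1.2 to -0.6, and above -0.6, with clinically important change as below -1.2.

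The cost is one sentence in the SAP and a matching line in the derivation specification. That specification is not among the documents, so whether it already uses the right sign should be checked. Passing one improving and one worsening patient from the table above through the code would confirm it. Data collection and the other analyses do not change.
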